## **9.7. Provision of Study Results to Investigators, Posting of Information on Publicly Available Clinical Trials Registers and Publication**

Where required by applicable regulatory requirements, an investigator signatory will be identified for the approval of the clinical study report. The investigator will be provided reasonable access to statistical tables, figures, and relevant reports and will have the

opportunity to review the complete study results at a GSK site or other mutually-agreeable location.

GSK will also provide the investigator with the full summary of the study results. The investigator is encouraged to share the summary results with the study subjects, as appropriate.

GSK will provide the investigator with the randomisation codes for their site only after completion of the full statistical analysis.

The results summary will be posted to the Clinical Study Register no later than eight months after the final primary completion date, the date that the final subject was examined or received an intervention for the purposes of final collection of data for the primary outcome. In addition, a manuscript will be submitted to a peer reviewed journal for publication no later than 18 months after the last subject's last visit (LSLV). When manuscript publication in a peer reviewed journal is not feasible, a statement will be added to the register to explain the reason for not publishing.

A manuscript will be progressed for publication in the scientific literature if the results provide important scientific or medical knowledge.

# 11. APPENDICES

## 11.1. Appendix 1: CHILDS-PUGH SCORE\*

Component	Score Given
	CCI

CCI - This section contained Clinical Outcome Assessment data collection questionnaires or indices, which are protected by third party copyright laws and therefore have been excluded.

### Childs-Pugh Classification

Childs-Pugh Class [CCI] = score [CCI]

Childs-Pugh Class [CCI] = score [CCI]

Childs-Pugh Class [CCI] = score [CCI]

\* Reference: Haozhu Chen, Guowei Lin. Practice of internal medicine. Edition 13. Beijing: People's Medical Publishing House, 2009:2082

## 11.2. Appendix 2: Estimated creatinine clearance rate (CLcr) Formula and Estimated Glomerular Filtration Rate (GFR) Equation

### CLcr using Cockcroft-Gault (CG) formula:

$$\text{CLcr} = [(140 - \text{Age}) \times \text{Ideal Body Weight (kg)}] / [72 \times \text{Scr (mg/dL)}]$$

Scr = Serum Creatinine in mg/dL; for female Multiplied by the coefficient of 0.85

Note: If actual body weight (ABW) is lower than ideal weight body (IBW), ABW should be used. Calculation Formula for IBW:

$$\text{(Male) IBW} = 50\text{kg} + 2.3\text{kg} \times [\text{Height (Inch)} - 60]$$

$$\text{(Female) IBW} = 45.5\text{kg} + 2.3\text{kg} \times [\text{Height (Inch)} - 60]$$

$$1\text{ Inch} = 2.54\text{cm}$$

### GFR Equation:

Glomerular filtration rate is estimated by Chronic kidney disease (CKD)-Epidemiology Collaboration (EPI) equation:

$$\text{GFR (mL/min per } 1.73 \text{ m}^2) = 141 \times \min(\text{Scr}/\kappa, 1)^\alpha \times \max(\text{Scr}/\kappa, 1)^{-1.209} \times 0.993^{\text{Age}} [ \times 1.018 \text{ if female} ] [ \times 1.159 \text{ if black} ],$$

[figure not shown]
where Scr is serum creatinine (mg/dl),  $\kappa$  is 0.7 for females and 0.9 for males,  $\alpha$  is  $-0.329$  for females and  $-0.411$  for males, min is the minimum of  $\text{Scr}/\kappa$  or 1, and max is the maximum of  $\text{Scr}/\kappa$  or 1

### 11.3. Appendix 3: Histological Score

Modified Knodell scoring system

Category	Score

CCI - This section contained Clinical Outcome Assessment data collection questionnaires or indices, which are protected by third party copyright laws and therefore have been excluded.
	

CCI - This section contained Clinical Outcome Assessment data collection questionnaires or indices, which are protected by third party copyright laws and therefore have been excluded.

## 11.4. Appendix 4: Lactic Acidosis Guidelines

Lactic acidosis and severe hepatomegaly with steatosis, including fatal cases, have been reported with the use of nucleoside analogues alone or in combination with other antiretrovirals. Most of these cases have been in women. Obesity and prolonged nucleoside exposure may be risk factors; however, cases have also been reported in subjects with no known risk factors.

Guidelines for management of symptomatic hyperlactatemia and asymptomatic hyperlactatemia are outlined in Section A and B below and are derived from the AACTG Lactic Acidosis Guidelines. Section C outlines venous lactate collection techniques.

### Section A. Symptomatic Hyperlactatemia

Symptomatic hyperlactatemia is defined as a clinical suspicion of hyperlactatemia characterised by new, otherwise unexplained and persistent ( $\geq 2$  weeks) occurrence of one or more of the following symptoms:

- Nausea and vomiting.
- Abdominal pain or gastric discomfort.
- Abdominal distention.
- Increased LFTs.
- Unexplained fatigue.
- Dyspnoea.

AND

Venous lactate level  $>2$  x ULN confirmed by repeat venous lactate analysis within 1 week and, if persistently elevated, arterial lactate with blood gas analysis.

If the repeat venous lactate is elevated confirmation with an arterial lactate specimen and arterial blood gas (pH, PO2, PCO2, bicarbonate, oxygen saturation) should be performed within 48 h. If the arterial specimen contains lactate at a level  $>2$  x ULN, the subject should be discontinued from the study and alternative therapy started. Subjects should be monitored weekly until signs and symptoms resolve. Hyperlactatemia should be followed until levels return to  $<2$  x ULN.

An elevated anion gap in a subject with metabolic acidosis suggests the diagnosis of lactic acidosis. It can be suspected when the sum of anions minus the sum of cations  $[(\text{Na}^+ + \text{K}^+) - (\text{Cl}^- + \text{HCO}_3^-)]$  exceeds 18 mEq/L (18 mmol/L) in the absence of other causes of increased anion gap such as renal failure, salicylate ingestion or other poisoning, or significant ketonemia (e.g., diabetic ketoacidosis, alcohol).

Management of symptomatic subjects with lactate levels of 1–2 x ULN is left to the discretion of the Investigator. As some of the symptoms are sufficiently vague (e.g., fatigue) to be present in everyone, serial repeat testing is encouraged with plans to modify the regimen if the lactate level rises to  $>2$  x ULN as outlined above.

## Section B. Asymptomatic Hyperlactatemia

In asymptomatic subjects, lactic acidosis will be defined as hyperlactatemia  $>4$  x ULN. Any subject with a lactate level  $>2$  x ULN but  $\leq 4$  x ULN, should be questioned closely for symptoms (described above) and have a repeat venous sample obtained in 1 week, and, if confirmed, subsequently at monthly intervals.

If the subject fulfils the definition for asymptomatic hyperlactatemia, repeat venous lactate should be obtained within a week with confirmation of a more than four-fold venous elevation in lactate by arterial lactate measurement and arterial blood gas (pH, PO2, PCO2, bicarbonate, oxygen saturation) within 48 h. If confirmed, the subject should be discontinued from the study and alternative therapy instituted. Hyperlactatemia should be followed until levels return to  $<2$  x ULN.

## Section C. Specimen Collection

Venous lactate levels are highly dependent on collection techniques. It is therefore recommended that the instructions below be followed closely. High lactate levels should be repeated for verification. If carefully collected, venous lactate level is equivalent to an arterial collection in most clinical situations. If it is not possible to collect the specimen without hand clenching or prolonged tourniquet time, an arterial lactate should be considered, as this will help exclude falsely elevated lactate levels.

Have subject sit, relaxed for 5 minutes prior to venepuncture.

1. Instruct subject not to clench the fist before or during the procedure and to relax the hand as much as possible.
2. If possible, do not use a tourniquet. If a tourniquet is necessary, then apply tourniquet lightly and draw lactate first before the other samples with the tourniquet still in place.
3. Collect the blood in a chilled gray-top (sodium fluoride-potassium oxalate) tube.
4. Place the specimen immediately on ice and send to the laboratory for immediate processing, preferably within 30 minutes of collection.
5. If random lactate is elevated, then repeat as above with the following additional subject instructions: no alcohol within 24 h, no exercise within 8 h, and no food or drink except water within 4 h of the draw.

LIST OF ABBREVIATIONS

Abbreviation	Description of Abbreviation
ADV	Adefovir
AE	Adverse event
ALT	Alanine aminotransferase
CFDA	China Food and Drug Administration
CHB	Chronic hepatitis B
95% CI	95% Confidence Interval
DNA	Deoxyribonucleic acid
ETV	Entecavir
HBeAg	Hepatitis B e antigen
HBsAg	Hepatitis B s antigen
HBV	Hepatitis B virus
HCV	Hepatitis C virus
INR	International Normalized Ratio
LAM	Lamivudine
LdT	Telbivudine
mITT	Modified Intent-to-treat (population)
NAs	Nucleos(t)ide analogues
PP	Per protocol (population)
PT	Prothrombin time
SA	Safety analysis (population)

Abbreviation	Description of Abbreviation
SAE	Serious adverse event
SAP	Statistical analysis plan
SD	Standard deviation
TDF	Tenofovir disoproxil fumarate
TEAE	Treatment-emergent adverse events
ULN	Upper limit of the normal range

Trademark Information

Trademarks of the GlaxoSmithKline group of companies
Hepododin

Trademarks not owned by the GlaxoSmithKline group of companies
Viread
Sebivo
Baraclude

1. INTRODUCTION

The purpose of this statistical analysis plan (SAP) is to describe the procedures to be used for analyzing and reporting the efficacy and safety for study 201213. It should be used in conjunction with the following documents: study protocol, case report form, and shells for tables, listings and graphs. This SAP is based on the final protocol (Version 3.0, March 27, 2016).

2. STUDY OBJECTIVE

2.1 Primary objective

- To evaluate the incidence of hepatocellular carcinoma (HCC) during 240-weeks of TDF 300mg QD treatment in Chinese CHB subjects with advanced fibrosis and compensated cirrhosis.
- To evaluate the rate of disease progression during 240-weeks of TDF 300mg QD treatment in Chinese CHB subjects with advanced fibrosis and compensated cirrhosis.

2.2 Secondary objective

- To evaluate the efficacy and safety of 240 weeks of TDF 300mg QD treatment in Chinese CHB subjects with advanced fibrosis and compensated cirrhosis.

3. STUDY DESIGN

3.1 Overall study design

This is a prospective, multi-centre, open-label, cohort study to investigate efficacy and safety of Tenofovir Disoproxil Fumarate (TDF) treatment in Chinese CHB subjects with advanced fibrosis and compensated cirrhosis. The study will enroll 186 subjects with a diagnosis of CHB and advanced fibrosis or compensated cirrhosis.

Screen phase (≤ 4 weeks): Written informed consent must be obtained from each subject prior to participation in the study. Subjects considered eligible to enroll in the study will be assessed at a screening visit as described in Table 1 to decide if they meet the study criteria. Between Screen visit and baseline visit, subjects will not receive investigational product.

Treatment phase: 186 subjects will be administered TDF 300 mg QD and undergo regular safety and efficacy assessments every 12 weeks for a total of up to 240 weeks (see Table 1). Subjects will be questioned about adverse events, concurrent medications, and study drug accountability; blood will be taken for hematology and biochemistry profiles; serum samples will be tested for HBV markers, and the prothrombin time will be measured. Serum samples will be collected at Week 12, 24, 36, 48, 60, 72, 84, and 96 and every 24 weeks thereafter and analyzed for HBV DNA levels at a central laboratory. Abdominal ultrasound, the prothrombin time and serum alpha-fetoprotein test will be performed every visit. If abdominal ultrasound reports a liver mass or nodule, CT or MRI will be performed. At baseline and Week 216, 100 of subjects will take liver biopsy to evaluate liver histological changes pre and post TDF treatment. All subjects will be followed through to Week 240.

Rescue treatment could be optionally initiated in subjects with unsatisfied response to TDF, at the discretion of the investigator if

- Subjects have confirmed virological breakthrough as defined by \geq one \log_{10} IU/mL increase in HBV DNA from nadir determined by two sequential HBV DNA measurements at least 1 month apart, or
- Subjects have HBV DNA ≥ 200 IU/ml at week 48 and afterwards have \leq one \log_{10} IU/mL decrease in HBV DNA at two consecutive visits, confirmed by a third visit at least one month apart.

Confirmation of HBV DNA test will require an additional visit to collect serum sample. To receive rescue treatment subjects must have investigational product (IP) compliance $> 80\%$ in the last regular visits period (usually 12 weeks). Add-on combination with a nucleoside agent (LAM, ETV or LdT) is acceptable rescue treatment in this study, as to investigator's decision. Before rescue

treatment, serum sample should be collected for resistance testing.

Subjects who reach primary endpoint (i.e. develop liver complications or HCC) may withdraw from study. Investigator and subjects can decide whether to continue study drug. Subjects who continue to take study drug will be followed as per the original schedule until Week 240. During the follow-up period, AEs, concomitant medication, vital signs, hepatitis B virus DNA, haematology, chemistry and prothrombin will be evaluated. Serum/plasma storage also will be conducted.

Supplementary study conduct information not mandated to be present in this protocol is provided in the accompanying Study Procedures Manual (SPM). The SPM will provide the site personnel with administrative and detailed technical information that does not affect subject safety.

3.2 Sample size

3.2.1 Sample size Assumptions

Sample sizes are chosen based on feasibility and precision because no hypothesis is tested in this study.

To decide the number of subjects for analysis, some precision calculations have been performed for the primary endpoint HCC incidence. In the retrospective analysis of GS-US-174-0102 and GS-US-174-0103 trials, HCC incidence over 7 years was approximately 4.5% among patients (23% of whom were Asian, 25 of whom were genotype B or C) with cirrhosis at baseline. Accordingly, we hypothesize that the accumulative incidence of HCC at 240 weeks will be 5% in Chinese compensated cirrhotic patients treated with TDF. The precision is calculated by the following:

$$Precision = Z_{1-\alpha/2} \sqrt{\frac{p(1-p)}{N}}$$

where Z is the critical value of normal distribution corresponding to the probability of $1-\alpha/2$ (corresponding to $(1-\alpha)*100\%$ confidence interval), and p is the percentage of patients who were diagnosed HCC during 240 weeks. Precision is half of the width of 95% confidence interval for the

point estimate. A sample size of 158 patients will allow us to estimate the confidence interval of the incidence with a margin of error at 3.4 % (0.016-0.084). Assuming a 15% drop out rate, 186 patients are to be recruited.

3.2.2 Sample Size Sensitivity

The sample size estimates are dependent upon the assumed incidence.

Different sample sizes and corresponding precisions are provided in the table below. It assumes the percentage of patients HCC is 5%.

P	1-p	Width (half CI)	N
5%	0.95	0.04	115
5%	0.95	0.034	158
5%	0.95	0.033	168
5%	0.95	0.032	179
5%	0.95	0.03	203
5%	0.95	0.02	457

4. ANALYSIS SET

- Modified Intent-to-treat (mITT) Population

The mITT population is defined as all recruited subjects who receive at least one dose of study medication.

- Per Protocol (PP) population

The PP population will consist of subjects in the mITT population who have no major protocol deviations that impact efficacy evaluation.

- Safety Analysis (SA) population

The SA population is defined as all subjects who receive at least one dose of study medication and have at least one post baseline safety assessment.

All efficacy endpoints will be analyzed using the mITT population and PP population will be used for primary endpoints. All safety endpoints will be analyzed using the SA population.

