### **1.3.1. Risk Assessment**

Potential Risk of Clinical Significance	Data/Rationale for Risk	Mitigation Strategy
Investigational Product (IP)		
Renal toxicity	Tenofovir is principally eliminated by the kidney. Renal impairment, including cases of acute renal failure and Fanconi syndrome (renal tubular injury with severe hypophosphatemia), has been reported with the use of VIREAD.	
 
• Exclusion of CHB patients with creatinine clearance <70 mL/min
 
• Monitor renal function every 12 weeks
 
• Dosing interval adjustment of VIREAD is recommended in all patients with creatinine clearance below 50 mL/min.
 
• Stopping criteria based on renal function with serum creatinine confirms >2.5 mg/dL have been clearly defined.(see section 6.3.2)
 

Bone events	Decreases in Bone mineral density (BMD) has been reported in adults and pediatric patients. The effects of VIREAD-associated changes in BMD and biochemical markers on long-term bone health and future fracture risk are unknown.	
 
• Monitoring the serum calcium and phosphate every 12 weeks
 
• In every regular visits, the information of bone related symptoms will be collected.
 
• Assessment of BMD and related treatment should be considered by the investigator's judgement.
 

Lactic acidosis/severe hepatomegaly with steatosis and lipodystrophy	Lactic acidosis/ severe hepatomegaly with steatosis, including fatal cases, have been reported with the use of nucleoside analogs, including VIREAD, in combination with other antiretrovirals.	
 
• Guidelines for management of lactic acidosis are outlined in Appendix 4.
 

Drug-Drug Interaction Potential	Since tenofovir is primarily eliminated by the kidneys, coadministration of VIREAD with drugs that reduce renal function or compete for active tubular secretion may increase	
 
• Estimated creatinine clearance will be assessed in all patients every 12 weeks during treatment with TDF
 
• TDF should be avoided
 

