## **8.3. Data Analysis Considerations**

### **8.3.1. Analysis Populations**

Three populations will be used in the analysis:

- Modified Intent to Treat (mITT) Population

The mITT population is defined as all randomised subjects who receive at least one dose of study medication.

- Per Protocol (PP) population

The PP population will consist of subjects in the mITT population with the exception of major protocol violators. Details on the definitions of major protocol violators will be included in the reporting and analysis plan (RAP).

- Safety Analysis (SA) population

The SA population is defined as all subjects who receive at least one dose of study medication and have at least one post baseline safety assessment.

All efficacy endpoints will be analysed using the mITT and PP population according to the treatment groups to which they were randomised. As this is a superiority study, the mITT population is the most conservative approach to statistical analysis; hence, the mITT population is of primary interest.

All safety endpoints will be analysed using the SA population according to the actual treatment they received.

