7.5 Safety analysis

Safety endpoints include adverse events, vital signs, laboratory assessments, physical examination,

and B-ultrasound. The analysis will be conducted in SA population.

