7.5.1 Adverse events

AEs will be classified into standardized medical terminology from the verbatim description (investigator term) using the Medical Dictionary for Regulatory Activities (MedDRA). Verbatim description and MedDRA level terms, including the system organ class, preferred term, and lower level term, for all AEs will be presented in the data listings. In table summaries, the denominator for percentages will be the number of subjects in the treatment group within the safety analysis population. AEs are coded according to (MedDRA) version 17.0.

TEAE is defined as AE occurred on or after the first dose date of study drug. TEAEs will be presented by system organ class and preferred term. The subject level incidence is only one occurrence of a preferred term/system organ class per subject. If a subject reports multiple AEs under the same preferred term, then the count of subject level incidences for that preferred term will only be incremented by one. If a subject reports multiple AEs under the same system organ class, then the count of subject level incidences for that system organ class will also only be incremented by one. System organ classes will be presented in descending order of total frequency of subject level occurrences. Within each system organ class, preferred terms are presented in the same descending order of total frequency of subject level occurrences.

An overall summary table of AE will be provided, including summaries of all AEs, all TEAEs, all treatment related TEAEs, all serious TEAEs, all treatment related serious TEAEs, all TEAEs leading to permanent discontinuation of study drug, all TEAEs leading to permanent discontinuation from the study, and all TEAEs that caused a change in dose or temporary interruption of study drug. Listings will be provided correspondingly.

All TEAEs and all serious TEAEs will be summarized by SOC and PT, and by intensity. All TEAEs will also be summarized by relationship to study drug.

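### The safety population requires an undefined post-baseline assessment, so a dosed subject lost before Week 12 can be left out of the adverse event and laboratory outputs

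*SAP*

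**What the plan says.** SAP section 4 (Analysis Set) admits to the SA population subjects who "receive at least one dose of study medication and have at least one post baseline safety assessment". Protocol 8.3.1 agrees: beyond a dose, subjects must "have at least one post baseline safety assessment". Neither document defines the term.

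The efficacy set has no such condition: "The mITT population is defined as all recruited subjects who receive at least one dose of study medication".

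The SA population governs safety reporting throughout the SAP:

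- Section 4: "All safety endpoints will be analyzed using the SA population".
- Section 7.5: "The analysis will be conducted in SA population".
- Section 7.5.1, for AE tables: "the denominator for percentages will be the number of subjects in the treatment group within the safety analysis population".
- Section 9: the section 5 tables (AEs, serious TEAEs, vital signs, laboratory) and Listings 5.1.1 to 5.5 are labelled SA.

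On timing, protocol 6.1 gives the first dose at the baseline visit, once all procedures are done, and the subject may then leave. SAP 3.1 has subjects "undergo regular safety and efficacy assessments every 12 weeks for a total of up to 240 weeks". Protocol Table 1 has no visit between baseline and Week 12 (±6 days).

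**The concern.** A safety set should be fixed by exposure to the drug. Here it is also fixed by something that happens after exposure and that harm can prevent. A subject who dies, or who stops and is never seen again, in the first 12 weeks may have no post-baseline assessment. On one reading of the rule, that subject is missing from both the numerator and the denominator of the AE and SAE tables.

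What is at stake is rare, early, serious harm. The protocol's risk table (1.3.1) lists renal toxicity including acute renal failure, and says of lactic acidosis and severe hepatomegaly with steatosis that cases, "including fatal cases, have been reported with the use of nucleoside analogs". In a single-arm study of 186 subjects such outcomes would be expected in very few people, if any, so one missing subject can change what is reported. The condition can also leave the safety outputs resting on fewer subjects than the efficacy outputs, although both sets begin from the same dosed subjects.

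**Working it through.** **1. The plan's own numbers.** Inputs from SAP 3.2.1 and protocol 8.2.1: p = 0.05, half-width e = 0.034, drop-out 15%.

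- N = p(1 − p)(z/e)² = 0.05 × 0.95 × (1.96/0.034)² = 157.8, rounded up to 158.
- Recruited = 158/0.85 = 185.9, rounded up to 186.

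Both stated figures reproduce. They supply the 186 and the 15% used below.

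**2. How many subjects could be affected.** The documents give no figure for loss before Week 12. Assume the 15% is spread evenly over 240 weeks.

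- Linear: 186 × 0.15 × 12/240 = 1.40.
- Constant hazard: 186 × (1 − 0.85^(12/240)) = 186 × 0.00809 = 1.51.
- If early loss ran at three times that rate (purely illustrative): 3 × 1.51 = 4.5.

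These counts cover subjects leaving for any reason. Those with a serious event and no assessment would be a subset.

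**3. Effect on common AEs.** Suppose x of N = 186 dosed subjects have the event and k subjects are excluded.

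- If every excluded subject had it, the rate falls by x/N − (x − k)/(N − k) = k(N − x)/[N(N − k)], which is at most k/N because x ≥ k.
- If none had it, the rate rises by xk/[N(N − k)], also at most k/N because x ≤ N − k.
- With k = 1.51 the bound is 1.51/186 = 0.8 percentage points.

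**4. Effect on a single rare event.**

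| | Reported | Rate | Exact 95% CI |
|---|---|---|---|
| All dosed subjects | 1/186 | 0.5% | 0.01% to 3.0% |
| That subject excluded | 0/185 | 0% | 0% to 2.0% |

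The intervals overlap heavily. What changes is whether the event is reported at all.

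**5. Two readings of the undefined term.**

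| Reading | Dosed subject lost before Week 12 with an event | Dosed subject lost before Week 12 without an event |
|---|---|---|
| Scheduled visit or measurement needed | Out, unless measured later or at an unscheduled visit | Out, unless measured later |
| AE, SAE or death report suffices | In | Out, unless measured later |

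On the upper reading, membership depends on attendance. On the lower reading it depends on having had an event, and the AE percentages are slightly inflated. Neither reading gives a set defined by exposure.

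**6. Where else the subject would appear.** SAP 7.1 bases disposition percentages on all enrolled subjects and includes adverse event among the discontinuation reasons. Table 3.1 (compliance and duration of drug) uses mITT. Neither shows the event term, seriousness or relatedness. The reasons listed in SAP 7.1 do not include death. Protocol 8.3.5.2 names deaths among the safety observations, yet the SAP section 9 index has no separate death table or listing.

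**The case against.** A reader might infer that everyone who dies or stops for toxicity before Week 12 is removed from every safety table. The documents do not support that, for these reasons.

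- **An event report may count.** AEs are collected from the start of treatment (protocol 6.3.8), SAEs are reported within 24 hours (6.3.10) and every death has its own form (6.3.5). SAP 7.5 lists adverse events among the safety endpoints. Treating a post-dose report as a safety assessment is reasonable, and no harm would then be hidden.
- **Subjects who stop are followed.** Protocol 4.4 and Table 1 footnote 3 require evaluation after permanent discontinuation, and 6.3.1 and 6.3.2 call for repeat tests after ALT or creatinine abnormalities. Most toxicity withdrawals would gain an assessment.
- **The named risks fit poorly.** Renal failure and lactic acidosis are recognised from laboratory values, and clinically significant local results go into the CRF (6.3.11). The risk table's lactic acidosis statement concerns use with other antiretrovirals, and Appendix 4 names prolonged exposure as a possible risk factor.
- **Not every output uses SA.** Disposition and exposure do not.

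A reader might also infer that an early death would count in the progression endpoint while vanishing from safety. Only liver-related death is a progression event (SAP 5.1), so that contrast is narrow.

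All of this stands and limits the point. It does not remove it. Follow-up helps only those who attend, and the generous reading is not written down. Under that reading, inclusion of early losses still turns on whether an event was reported. There is no comparator arm, so no between-group contrast is distorted.

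**Conclusion.** The concern holds as a weakness of definition with a small expected effect. Both documents condition the safety set on an undefined post-dose assessment, with the first scheduled one at Week 12. A dosed subject who dies or never returns before any assessment can therefore be left out of the SA-labelled AE, SAE and laboratory outputs on a visit-based reading. On the broader reading, only early losses without an event drop out.

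The size rests on assumption. About 1.4 to 1.5 of 186 subjects would leave before Week 12 if the planned 15% drop-out is uniform, and those with a serious event and no assessment would be fewer. Common AE rates would shift by at most about 0.8 percentage points. The practical consequence is confined to a rare early event, where 1/186 could become 0/185. The documents do not show that any event would in fact be lost. The point is a cheap improvement and does not threaten the study's conclusions.

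**What to change.** In SAP section 4 and protocol 8.3.1, define the SA population as every subject who took one or more doses of TDF. Use it as the denominator for AEs, SAEs and deaths. For laboratory and vital-sign changes, use the number of subjects with both a baseline and a post-baseline value, and print that n in each table.

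The cost is one line in each document and no new data, since AEs, SAEs and deaths are already recorded from first dose. On present definitions the SA and mITT sets would then contain the same subjects. The downside is that one or two subjects with little follow-up enter the denominator and very slightly dilute the percentages.

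A weaker alternative is to keep the condition and state that any AE, SAE or death report after the first dose meets it. That keeps early events in the tables but still drops early losses without an event, so the all-dosed definition is preferable.
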